## 5 CRITERIA FOR EVALUATION

### 5.1 Primary Endpoints

The co-primary endpoints will be feasibility and acceptability of the Empower Neuromodulation System as a daily therapy for GAD. Feasibility will be evaluated via treatment adherence (% treatment sessions completed out of the total possible) and acceptability will be evaluated via usability as assessed by the System Usability Scale (SUS) questionnaire. As part of this study, it is critical to identify an appropriate sham treatment prior to initiating a follow-on pivotal study, so all feasibility and acceptability endpoints will be evaluated for [REDACTED] treatments in this study. The effect of treatment group on these co-primary endpoints will also be evaluated.

### 5.2 Secondary Endpoints

The following secondary endpoints will be evaluated:

- Feasibility: For each treatment group, the percentage of treatment sessions that provide effective nerve stimulation as assessed via participant-reported confirmation of tingling sensation
- Acceptability: For each treatment group, the overall satisfaction with treatment (via 100-mm VAS)
- Effectiveness:
  - Effect of treatment group on change in clinician-assessed anxiety severity (via HAM-A)
  - Effect of treatment group on change in weekly participant-reported anxiety severity (via BAI)
  - Effect of treatment group on change in participant-reported GAD symptoms (via GAD-Q-IV)
  - Effect of treatment group on change in daily self-reports for anxiety severity (via 100-mm VAS)
  - Effect of treatment group on change in self-reports of anxiety severity immediately after vs. before treatment (via 100-mm VAS)
  - Effect of treatment group on change in daily self-reports for anxiety interference with daily living (via 100-mm VAS)
  - Effect of treatment group on medication use (via self-reports)
  - Effect of treatment group on change in clinician-assessed depression severity (via HAM-D)
  - Effect of treatment group on change in participant-reported depression severity (via PHQ-9)
  - Effect of treatment group on change in participant-reported PTSD severity (via PCL-5)
  - Effect of treatment group on change in sleep quality (via PSQI survey)

- Effect of treatment group on change in quality of life (via SF-12 survey)
- Blinding: For each treatment group, the blinding index and 95% confidence interval (via Bang et al. blinding assessment method)

All of these secondary endpoints provide valuable information on the effectiveness of the Empower Neuromodulation System for GAD treatment as well as the acceptability to the intended patient population.

### 5.3 Safety Evaluations

Safety evaluations will include the incidence and severity of device-related AEs and the incidence and severity of SAEs (regardless of relationship to the device).

## 6 PARTICIPANT SELECTION

### 6.1 Study Population

The study population is adults with generalized anxiety disorder (GAD). Participants who meet all of the inclusion and none of the exclusion criteria will be eligible to be randomized for full participation in the study.

### 6.2 Inclusion Criteria

1.  $\geq 19$  years old
2. Current diagnosis of GAD per DSM-5 via M.I.N.I. assessment by clinician
3. HAM-A  $\geq 18$
4. Negative urine pregnancy test at screening (females only)
5. Able to provide informed consent
6. Capable and willing to follow all study-related procedures

### 6.3 Exclusion Criteria

1. Has current (past 30 days) psychotic or bipolar disorder, homicidal ideation, psychiatric hospitalization, or moderate/severe SUDs per clinician assessment via M.I.N.I.
2. HAM-D  $\geq 18$
3. PCL-5  $\geq 34$
4. Exhibits suicidal intent as confirmed on the Columbia-Suicide Severity Rating Scale-Revised (C-SSRS-R) with a “Yes” response to question 4 or question 5, or to question 6 in the past 3 months.
5. Changes in psychoactive medications in the past 30 days (including but not limited to psychotropic medications, thyroid hormone medication, steroids), with the exception of benzodiazepines
6. If regularly taking benzodiazepines, has had changes in benzodiazepine dosing in the past 30 days or average use  $> 2$  days per week
7. Psychotherapy was initiated or discontinued in the past 30 days or psychotherapy modality was changes in the past 30 days
8. Has a history of epilepsy or a seizure disorder

9. Has been diagnosed with peripheral nerve damage of the arm or hand or has numbness or tingling in the arm or hand at least weekly
10. Is currently pregnant or breastfeeding, has been pregnant within the past 6 months or intends to become pregnant during the study period
11. Currently has an active implant and/or an electrical or neurostimulator device, including but not limited to cardiac pacemaker or defibrillator, vagal neurostimulator, deep brain stimulator, spinal stimulator, sacral stimulator, bone growth stimulator, or cochlear implant
12. Has an electrically conductive metal object (e.g. jewelry) that cannot be removed from [REDACTED] and will directly contact the gel electrodes of the Empower Neuromodulation System at either anatomic location
13. Has an open incision, wound, scar, active infection or otherwise compromised skin at the [REDACTED] and will directly contact the gel electrodes of the Empower Neuromodulation System at either anatomic location
14. Does not have daily access to an electrical outlet for charging the investigational device and associated smartphone
15. Has used of an investigational drug/device therapy within the past four weeks
16. Unable to provide informed written consent
17. Has any medical condition that would, in the opinion of the investigator, make the participant ineligible

## 7 CONCURRENT MEDICATIONS

Each participant should be maintained on the same psychotropic/psychoactive medications throughout the entire study period, as medically feasible, with no introduction of new chronic therapies.

### 7.1 Allowed Medications and Treatments

As outlined in the inclusion criteria, at the time of enrollment, participants may be taking scheduled antianxiety, psychotropic, or psychoactive medications (>30 days on a stable dose preceding enrollment) or benzodiazepines ( $\leq 2$  days per week). Participants may also be in psychotherapy as long as no changes have been made in psychotherapy in the 30 days preceding study enrollment. Only treatments and medications noted in the exclusion criteria described above will be considered a protocol violation. All other medications are allowed.

## 8 STUDY PROCEDURES

### 8.1 Method of Assigning Participants to Treatment Groups

This is a randomized, controlled study. At enrollment participants will be randomized (1:1, [REDACTED] to the active or sham treatment group. Men and women will be randomized separately to ensure that the distribution of men and women in the active and sham arms are consistent. Women account for approximately 64% of American adults with GAD. Thus, to ensure that we enroll a study cohort that is both representative of the American patient population and provides a sufficient sample size of both sexes to

exploratorily evaluate sex as a biological variable, we will enroll a maximum of 21 women and a maximum of 12 men.

[figure not shown]
Participants will also be randomized for the body side that they should apply stimulation to first [REDACTED]

## 8.2 Investigational Device

### 8.2.1 Device Description

The investigational device is called the Empower Neuromodulation System (**Fig. 3**).

### 8.2.2 Device Description

[figure not shown]
### 8.2.3 Intended Use

The Empower Neuromodulation System is intended to provide transcutaneous electrical nerve stimulation to reduce anxiety.

### 8.2.4 Technical Specifications

[figure not shown]

### 8.2.5 User Interface

### 8.2.6 Participant-Contacting Materials

#### 8.2.6.1 Gel Electrodes

#### **8.2.6.2 Controller**

### **8.3 Measures of Compliance**

The device keeps a log of when the participant administers a treatment session and the duration of each session. This data is transmitted to the smartphone via Bluetooth at the end of each treatment session.

## **9 STUDY PROCEDURES AND GUIDELINES**

A Schedule of Events representing the required testing procedures to be performed for the duration of the study is diagrammed in Appendix 1.

Prior to conducting any study-related activities, written informed consent and the Health Insurance Portability and Accountability Act (HIPAA) authorization must be signed and dated by the participant. Assent must also be obtained prior to conducting any study-related activities.

### **9.1 Clinical Assessments**

#### **9.1.1 Concomitant Medications**

All concomitant medication and concurrent therapies will be documented at Screening. Dose, route, unit frequency of administration, and indication for administration and dates of medication will be captured.

### 9.1.2 Demographics

Demographic information (date of birth, gender, race, ethnicity) will be recorded at Screening.

### 9.1.3 Medical History

Relevant medical history, including history of current disease, other pertinent psychological history (e.g. depression, PTSD, etc.), and information regarding underlying diseases will be recorded at Screening.

### 9.1.4 Physical Examination

An abbreviated physical examination as needed to determine eligibility (specifically for evaluating the exclusion criteria for jewelry that cannot be removed and open wounds at the [REDACTED] will be performed by a study clinician at Screening. Site staff will also measure [REDACTED] participants randomized to the active treatment group.

### 9.1.5 Psychiatric Examination

An abbreviated psychiatric examination as needed to determine eligibility will be performed by either the investigator or qualified staff (MD, NP, or PhD) at screening. The Mini-International Neuropsychiatric Interview (M.I.N.I.) will be used to evaluate the DSM-5 criteria for GAD and other psychiatric disorders that are in the inclusion and exclusion criteria. The Columbia-Suicide Severity Rating Scale-Revised (C-SSRS-R) will be used to evaluate suicidality risk at each clinical visit.

### 9.1.6 Medical chart review

The participant will be asked about the following, and if available, the participant's medical chart will also be reviewed to determine if the participant has been diagnosed with any of the following:

- Epilepsy or seizure disorder
- Peripheral neuropathy or nerve damage of the upper extremities

The participant will be asked about the following, and if available, the participant's medical chart will be reviewed to determine if the participant has any of the following:

- Has used an investigational drug or device within the past four weeks
- Has implanted electrical and/or neurostimulator device (e.g. pacemaker, defibrillator, vagal neurostimulator, deep brain stimulator, spinal stimulator, sacral stimulator, bone growth stimulator, or cochlear implant)

### 9.1.7 Surveys

Throughout the study, the participant will provide responses and complete surveys that cover medication use, skin tingling during treatment, anxiety, depression, sleep quality, and quality of life. Daily surveys (medication use, skin tingling during treatment, anxiety

severity and interference with daily living) and weekly surveys (BAI) will be completed on the Empower app. Surveys will be completed at the same time as Empower treatment (the participant will be guided by the app as to when each survey is to be completed). Surveys conducted at Visits 1 and 3 (GAD-Q-IV, PHQ-9, PSQI, and SF-12) will be completed electronically or on paper. At each clinic visit, the participant will complete the daily and weekly surveys if they have not been completed for that day/week. At the final clinic visit, the participant will also complete the following electronic or paper-based surveys: usability survey (SUS), rating of overall satisfaction with treatment (100-mm VAS), blinding assessment, and a Final Study Questionnaire that includes questions regarding feedback on device features, device comfort and tolerability, and marketing questions.

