### 4.4 Study Overview

This is a single site, sham-controlled, double-blinded trial. The overall study goal is to evaluate the feasibility and acceptability of the Empower Neuromodulation System as a daily therapy for GAD patients. The total duration of participant participation will be six weeks (**Fig. 2**), and the total duration of the study is expected to be 9 months. Screening data will be reviewed to determine participant eligibility. Participants who meet all of the inclusion criteria and none of the exclusion criteria will be eligible to be randomized.

At enrollment, participants will be randomized (1:1) to either the active treatment arm [REDACTED] or the sham treatment arm [REDACTED]. Participants and clinician assessors will be blinded. For each enrollee's 6-week participation in the study, the participant will be instructed to self-administer [REDACTED]

[REDACTED] and complete daily surveys (self-reports on anxiety levels, medication use, and skin tingling felt during treatment) on the Empower app (on the provided smartphone). Weekly, the participant will be prompted to complete the BAI survey

**Figure 2.** Study outline. This 6-week study will include three study visits. For the duration of the study, participants will self-administer twice daily treatment sessions at home with the Empower Neuromodulation System and complete daily and weekly surveys. At Visits 1 and 2, clinician assessments will be administered and participants will complete surveys. The study completion visit will also include a usability survey and Study Completion Questionnaire.

on the Empower app. At the enrollment visit (Visit 1) and the final study visit (Visit 3), the participant will be assessed by one of the study clinicians for anxiety (HAM-A) and depression (HAM-D). At these study visits, the participant will also complete the following surveys on paper or electronically: PCL-5 GAD-Q-IV, PHQ-9, PSQI, and SF-12. At all clinic visits, the participant will be assessed for suicidality via the Columbia-Suicide Severity Rating Scale-Revised (C-SSRS-R).

Once enrolled and trained on device and app use, the participant will be instructed to conduct treatment sessions and complete surveys [REDACTED]

The Empower Neuromodulation System (which includes a smartphone with

Empower app) will be loaned to each participant for the duration of his/her participation in the study.

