#### ***9.1.7.1 Daily Surveys***

The daily survey questions will be completed on the Empower app and include questions about non-scheduled anxiety medication use (e.g. benzodiazepine dose taken over the past 24 hours and day/time of last dose), anxiety severity over the past 24 hours, anxiety interference with daily life over the past 24 hours, and anxiety severity at the present time. For anxiety severity, the participant will be asked to rate it on a 100-point visual analog scale (VAS) [0="No anxiety at all" through 100="Severe Anxiety"]. For anxiety interference with daily life, the participant will be asked to rate it on a 100-point visual analog scale (VAS) [0="Not at all" through 100="Extreme"].

The app will guide the participant to complete the daily survey prior to self-administering the first treatment session of each calendar day. Immediately after the session, the participant will also be asked about anxiety severity at the present time and if a tingling sensation was felt on the skin at the site of stimulation application to confirm effective nerve stimulation.

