#### 15.4 Analysis of Secondary Endpoints

Secondary endpoints will be analyzed via the methods described below. Unless otherwise noted, for daily and weekly metrics, we will use a random-intercept linear mixed model with restricted maximum likelihood to compare results between the active and sham treatment groups. As a secondary analysis for each of these endpoints, we will evaluate the correlations for duration since last benzodiazepine dose and dose amount vs. the endpoint. If this relationship is significant for an endpoint, we will include time since last dose in our statistical analysis.

Feasibility: Effective nerve stimulation: We will calculate effective nerve stimulation (treatment sessions that elicit skin tingling as a percentage of total treatment sessions) for each participant. We will also compare effective nerve stimulation between the active and sham treatment groups (t-test).

Acceptability: Overall satisfaction with treatment: We will compare overall satisfaction with treatment scores between the active and sham treatment groups (t-test).

Safety: We will tabulate AEs across all participants. This will include tabulating the number of participants for whom the event occurred, the rate of occurrence, and the severity and relationship to the study device.

Effectiveness: Change in HAM-A score: We will compare the change in HAM-A score between the active and sham treatment groups (t-test).

Effectiveness: Change in GAD-Q-IV score: We will compare the change in GAD-Q-IV score between the active and sham treatment groups (t-test).

Effectiveness: Change in BAI score: We will compare the change in BAI score between the active and sham treatment groups (mixed models).

Effectiveness: Change in daily anxiety severity self-report: We will compare the change in daily anxiety severity scores between the active and sham treatment groups (mixed models).

Effectiveness: Change in daily anxiety interference self-report: We will compare the change in daily anxiety interference scores between the active and sham treatment groups (mixed models).

Effectiveness: Change in anxiety severity self-report as an immediate result of treatment: We will compare the short-term effect of Empower treatment on anxiety severity score (% change for post-treatment score vs. pre-treatment score) (repeated measures ANOVA with Tukey correction, active vs. sham treatment group).

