Effectiveness: Medication use: We will calculate average benzodiazepine use per week. We will compare medication use between the active and sham treatment groups (mixed models).

Effectiveness: Change in HAM-D score: We will compare the change in HAM-D score between the active and sham treatment groups (t-test).

Effectiveness: Change in PHQ-9 score: We will compare the change in PHQ-9 score between the active and sham treatment groups (t-test).

Effectiveness: Change in PCL-5 score: We will compare the change in PCL-5 score between the active and sham treatment groups (t-test).

Effectiveness: Change in PSQI score: We will compare the change in PSQI score between the active and sham treatment groups (t-test).

Effectiveness: Change in SF-12 score: We will compare the change in SF-12 score between the active and sham treatment groups (t-test).

Blinding: We will statistically assess blinding for the active and sham treatment groups using the blinding index from Bang et al.

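### The daily and weekly app surveys are tied to treatment sessions, so completeness of benzodiazepine and anxiety reports depends on adherence, and weekly benzodiazepine use may be undercounted in the less adherent arm

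*Combined protocol and SAP*

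**What the plan says.** Section 9.1.7 sets the general rule for the app surveys: "Surveys will be completed at the same time as Empower treatment". Section 9.1.7.1 makes it specific: "The app will guide the participant to complete the daily survey prior to self-administering the first treatment session of each calendar day". That survey asks about non-scheduled anxiety medication ("benzodiazepine dose taken over the past 24 hours and day/time of last dose"), 24-hour anxiety severity and interference, and present anxiety. Section 9.1.7.2 places the BAI before the first session of each calendar week.

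There is one stated route outside treatment, in 9.1.7: "At each clinic visit, the participant will complete the daily and weekly surveys if they have not been completed for that day/week".

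For the analysis, Section 15.4 says of medication use "We will calculate average benzodiazepine use per week", compared between arms by mixed models. More generally, "for daily and weekly metrics, we will use a random-intercept linear mixed model with restricted maximum likelihood". Section 15 gives no denominator for the weekly average and no rule for unreported days or other missing data.

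Concomitant medication is recorded at Screening (9.1.1) and appears only under Visit 1 in Section 10 and Appendix 1. In the readable text the app survey is therefore the only planned source of benzodiazepine use during the study.

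**The concern.** A participant who starts no session on a given day has no planned daily report for that day. Such days are foreseen. Section 9.1.11 tells participants with irritated skin to pause treatment, and Sections 12.1 and 12.3 name less than one session per two weeks as non-compliance. Someone at that floor could have session-linked reports on 3 of 42 days.

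Adherence is a co-primary endpoint compared between arms (5.1, 15.3). If it differs, so will the completeness of four of the twelve secondary effectiveness endpoints: daily anxiety severity, daily interference, BAI and medication use. For benzodiazepine use the direction is predictable if unreported days are read as days without use, because the arm that treats less would appear to take less medication. For the anxiety series the risk is informative missingness. A mixed model uses the available records and is valid if missingness is explained by the observed data, but not if participants skip treatment because of how they feel that day. Section 15.4 also examines time since last dose and dose amount against each daily and weekly endpoint, so the same gaps carry into that analysis.

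**Working it through.** The plan gives no expected adherence, survey completeness or undercount, so there is no figure to reproduce. The following is an illustration.

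**Inputs**
- From the documents: two sessions a day (4.4: "participants will self-administer twice daily treatment sessions at home with the Empower Neuromodulation System"), and six weeks, or 42 days.
- Assumed: true use of 2 days/week in both arms (regular users averaging more than this are excluded at entry), so p = 2/7 per day. The share of days reported, c, is 90% in one arm and 70% in the other. A report is taken to describe the day on which it is made.

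**1. From session adherence to days reported.** A day is lost only if neither session is started. If misses cluster by day, c equals session adherence a. If the two sessions are missed independently, c = 1 − (1 − a)².
- a = 0.90: 1 − 0.10² = 0.99
- a = 0.70: 1 − 0.30² = 0.91

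**2. Unreported days counted as no use.** Recorded use = 2c.
- Clustered misses: 2 × 0.90 = 1.8 and 2 × 0.70 = 1.4; 1.4/1.8 − 1 = −22%.
- Independent misses: 2 × 0.99 = 1.98 and 2 × 0.91 = 1.82; 1.82/1.98 − 1 = −8%.

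**3. Adding the last-dose item to the sum.** The status of an unreported day is recovered if no later dose falls between it and the next report, that report day included. The probability is q = (1 − p)c / [1 − (1 − p)(1 − c)].
- c = 0.90: q = 0.643/0.929 = 0.692; use = 2 × (0.90 + 0.10 × 0.692) = 1.94
- c = 0.70: q = 0.500/0.786 = 0.636; use = 2 × (0.70 + 0.30 × 0.636) = 1.78

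A simulation of 40,000 participants over 42 days gives 1.93 and 1.77. These are slightly lower because the last days of the study have no later report. The false gap falls from 0.4 to 0.16 days/week.

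**4. Rate per reported day.** If missingness is unrelated to use, 2c/c = 2.0 in both arms. Now let a report be twice as likely to be missed on a day of use. The overall missing share is m = 1 − c, and the missing probability on a day of use is 2m/(5/7 + 2 × 2/7) = 14m/9.
- c = 0.90: 14 × 0.10/9 = 0.156; 2 × (1 − 0.156)/0.90 = 1.88
- c = 0.70: 14 × 0.30/9 = 0.467; 2 × (1 − 0.467)/0.70 = 1.52

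| Definition of weekly use (true value 2.0) | 90% of days | 70% of days | False gap |
|---|---|---|---|
| Sum of reported days | 1.8 | 1.4 | 0.4 |
| Sum plus last-dose recovery | 1.93 | 1.77 | 0.16 |
| Per reported day, missingness unrelated to use | 2.0 | 2.0 | 0 |
| Per reported day, twice as likely missed on days of use | 1.88 | 1.52 | 0.36 |

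**5. A trap in the repair.** Adding recovered doses to the numerator while dividing by reported days only gives 1.93/0.90 = 2.14 and 1.77/0.70 = 2.53. That is a false gap of 0.39 in the opposite direction. The known dose-free days must enter the denominator too. The share of days with known status is c + (1 − c)q, or 0.969 and 0.891. Then 1.94/0.969 and 1.78/0.891 both return 2.0 when missingness is unrelated to use.

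**The case against.** The strongest case on the other side has five parts.

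- **No zero rule is stated.** A reader might infer from 15.4 that an unreported day counts as a day without use, so that undercounting is certain. The plan does not say so. A per-reported-day average is equally compatible with its wording, and it is unbiased if missingness is unrelated to use. This stands, and the point is conditional for that reason.
- **Surveys may be possible without a session.** A reader might infer that data are collected only alongside treatment. Section 9.1.7 provides the clinic-visit catch-up, and 9.1.7.1 and 9.1.7.2 state an order without saying that the survey is locked otherwise. Text in 4.4, 9.1.8 and 9.1.9 is redacted, so a separate prompt cannot be ruled out. This stands as a limit, but no readable text provides such a prompt, and the catch-up covers only the visit's own day or week.
- **The loss is smaller than session adherence suggests.** This stands. With independent misses, 90% versus 70% of days reported would need session adherence of about 68% versus 45% (1 − √0.10 and 1 − √0.30). The BAI is lost only when a whole calendar week has no session. Non-users also dilute the absolute gap in group means, though not the ratio.
- **No arm difference in adherence is predicted.** Sections 5.1 and 15.3 say only that it will be compared. This stands.
- **The stakes are modest.** These are secondary endpoints in a 30-person pilot, and session adherence is logged and compared, so a difference between arms would be visible. Seeing it would not restore the missing reports.

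**Conclusion.** The point holds in conditional form. In the readable text, a day without a session has no planned daily report apart from clinic-visit catch-up, so completeness of these secondary endpoints depends on adherence. Weekly benzodiazepine use may be undercounted in the less adherent arm under either of two conditions: unreported days are treated as no use, or reports are missed more often on days of use. With 90% versus 70% of days reported, the false reduction ranges from none to 22%, depending on the definition and the missingness. It is about 8% under the zero rule if those percentages are session adherence and misses are independent. Reporting shares, true use and the missingness ratio are all assumptions.

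The documents do not establish that undercounting will occur, that adherence will differ by arm, or that the daily anxiety comparison is biased. The co-primary endpoints are unaffected. This is a low-cost improvement, worth making because Section 5.1 looks ahead to a pivotal study that might reuse the same capture method.

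**What to change.** 1. **Sections 9.1.7 to 9.1.7.2.** Have the app prompt the daily survey every calendar day and the BAI every calendar week, whether or not a session is started. Keep the present-anxiety and tingling items that surround a session tied to sessions. If a redacted passage already provides this, align 9.1.7 with it.
2. **Section 15.4, medication use.** State that unreported days are not counted as no use, and compute weekly use over days with known status. If last-dose dates are used to fill gaps, add both the dose days and the known dose-free days to the denominator.
3. **Section 15.4, reporting.** Report survey completeness by arm beside these endpoints.

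Items 2 and 3 change analysis wording only. Item 1 needs a small app change and slightly more prompting of participants. The weekly rate still assumes that days with known status are representative. Item 1 reduces reliance on that assumption but does not remove it, because prompted surveys can still go unanswered.
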